9.4.2. Safety Analyses

The safety analysis will be performed using the safety population based on a whole study and different periods separately and will be fully defined in the SAP. The safety parameters will include AEs, clinical laboratory measurements including fasting T3 and T4 (both total and free

Armour Thyroid

T3 and T4 taken prior to study intervention dose that day), vital sign values, ECG parameters, and physical examination findings. For each safety parameter of the clinical laboratory, vital sign, and ECG parameters, the last non-missing safety assessment before the first dose of study intervention will be used as the baseline for all analyses of that safety parameter.

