**Figure 4-1**      **3014-201-002 Study Schematic**

\* If a participant undergoes up to the maximum of 3 additional dose titrations starting at Week 18, the Titration Period may extend up to Week 36; therefore, the Stabilization Period may extend from Week 36 to Week 48 (remaining 12 weeks in duration). The Primary Endpoint will be measured at the end of the Titration Period and the end of the Stabilization Period.

During the Titration Period, study visits are split into parts A and B (i.e., Visit 3a, Visit 3b, Visit 4a, Visit 4b) to allow for any dose titrations:

- Visits 3a and 4a are mandatory for all participants. Study assessments, including bloodwork for total T3, TSH, and study intervention dispensing will be performed.
- Visits 3b and 4b are only required for participants needing a dose titration based on the data obtained from Visits 3a and 4a, respectively. A limited number of assessments and study intervention dispensing will be performed.

Visit 5 is designed as a transition visit between the Titration and Stabilization Periods and may consist of a subset of visits (starting with Visit 5a [Week 18] and extending to Visit 5g [Week 36], as needed). The last visit within Visit 5 serves as both the end of the Titration Period and the beginning of the Stabilization Period.

- Participants with TSH levels within normal reference range at Visit 5a may enter the Stabilization Period (i.e., their next visit will be Visit 6).
- If participants' TSH levels are out of normal reference range at Visit 5a, participants' doses can be up- or down-titrated per the Investigators' interpretation until their TSH levels are within the normal reference range by continuing the Titration Period

beyond Week 18. If the Titration Period is continued, the participants' doses can be up- or down-titrated approximately every 6 weeks until their TSH levels have normalized for up to a maximum of 3 additional titrations (including the titration at Visit 5b). Once their TSH levels are within the normal reference range, participants can enter the Stabilization Period. Participants whose TSH levels have not normalized after the maximum of 3 additional titrations will not enter the Stabilization Period.

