- Participants who need dose titration beyond Week 18 will complete a study visit approximately every 6 weeks to determine if their TSH levels are within the normal reference range. At these visits, they will have the same assessments performed as those performed at Visit 5a including study intervention dispensing. These assessment visits will be labeled sequentially 5c (Week 24), 5e (Week 30), and 5g (Week 36), as needed.
- Participants who need dose titration beyond Week 18 will also complete a study visit for additional study intervention dispensing. These study intervention visits will be labeled sequentially as 5b (Week 19), 5d (Week 25), and 5f (Week 31), as needed. Visit 5d and 5f will have all the same assessments and activities performed as Visit 5b.

The Titration Period is at least 18 weeks in duration. Depending on whether a participant requires additional dose titration after Visit 5a, the Titration Period may end at Week 18, 24, 30, or 36 (up to a maximum of 3 additional titrations are allowed starting at Visit 5b).

The Stabilization Period is 12 weeks in duration. Depending on whether a participant requires additional dose titration after Visit 5a, the Stabilization Period may end at Week 30, 36, 42, or 48. If a participant undergoes the maximum of 3 additional dose titrations starting at Week 5b, the Stabilization Period would be from Week 36 to Week 48.

Visit 6 may be at Week 24, 30, 36, or 42 depending on the number of additional titrations needed after Visit 5a. Visit 7 may be at Week 30, 36, 42, or 48 depending on the number of additional titrations needed after Visit 5a.

**Table 4-1** Schedule Activities

3014-201-002 Schedule of Activities											
	Screening	Titration Period (Week 0 to Week 18 a )							Stabilization Period (Week 18 a to Week 30 c )		Early Termination
		Visit 1	Visit 2	Visit 3a	Visit 3b d	Visit 4a	Visit 4b d	Visit 5a e	Visit 5b d,e	Visit 6 f	Visit 7 g
Visit Number	Visit 1										
Study Week	-3 to 0	0	6	7	12	13	18 d	19	24	30	
Visit Window	---	±3 days	±3 days	±3 days	±3 days	±3 days	±3 days	±3 days	±3 days	±3 days	
Informed consent	X										
Randomization		X									
Inclusion/exclusion	X	X									
Demographic data	X										
Medical history	X										
AEs	X	X	X	X	X	X	X	X	X	X	X
Clinical laboratory b,h,n	X	X	X		X		X		X	X	X
Vital signs b,i	X	X	X	X	X	X	X	X	X	X	X

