## **9.0**

## **EXTENT OF EXPOSURE AND TREATMENT COMPLIANCE**

### **9.1**

### **EXTENT OF EXPOSURE**

Exposure to the study treatment for the Safety and Safety-T3 Populations during the double-blind treatment period will be summarized for treatment duration, calculated as the number of days from the date of the first dose of double-blind investigational product taken to the date of the last dose taken, inclusive. Descriptive statistics (number of participants, mean, SD, minimum, median, Q1, Q3 and maximum) will be presented by treatment group.

Mean daily dose (by period and overall mean) for the study treatment will be summarized using descriptive statistics (number of patients, mean, SD, median, minimum, Q1, Q3 and maximum). Overall modal daily dose and final daily dose will be summarized by the number and percentage of patients with a pre-specified dose.

[figure not shown]
*Patient-years*, defined as exposure to the study treatment in years, will be summarized by treatment for the Safety and Safety-T3 Populations.

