## **10.4 ADDITIONAL AND EXPLORATORY EFFICACY ENDPOINTS**

## **11.0 SAFETY ANALYSES**

The safety analysis will be performed on the Safety and Safety-T3 Populations. The safety parameters will include AEs, clinical laboratory measurements including fasting T3 and T4 (total T3, total T4, free T3 and free T4), vital sign values, ECG parameters, and physical examination findings. For each safety parameter of the clinical laboratory, vital sign, and ECG parameters, the last non-missing safety assessment prior to or on the first dose of study intervention will be used as the baseline for all analyses of that safety parameter. Continuous variables will be summarized by number of patients and mean, SD, median, minimum, and maximum values. Categorical variables will be summarized by number and percentage of patients.

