### **11.1 ADVERSE EVENTS**

AEs will be coded using the Medical Dictionary for Regulatory Activities (MedDRA), Version 19.0 or newer.

An AE will be considered a TEAE if:

- The AE began on or after the date of the first dose of study intervention; or
- The AE was present before the date of the first dose of study intervention, but increased in severity or became serious on or after the date of the first dose of study intervention

An AE that occurs more than 35 days after the last dose of study intervention will not be counted as a TEAE.

An AE will be considered a TESAE if it is a TEAE that additionally meets any SAE criteria.

The number and percentage of participants reporting TEAEs in each study intervention group will be tabulated by system organ class and preferred term and by system organ class, preferred term, and severity.

The number and percentage of participants reporting treatment related TEAEs in each study intervention group will be tabulated by system organ class and preferred term. If more than 1 AE is coded to the same preferred term for the same participant, the participant will be counted only once for that preferred term using the most severe and most related occurrence for the summarizations by severity and by relationship to study intervention.

Summary tables will be provided for participants with SAEs and participants with AEs leading to discontinuation if 5 or more participants reported such events. Listings of all AEs, SAEs, and AEs leading to discontinuation by participant will be presented.

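### SAP 11.1 reports adverse events as crude participant percentages although follow-up length depends on TSH response, and visible Section 11 does not carry over the protocol's by-period analysis for AEs

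*SAP*

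**What the plan says.** **Summary measure.** SAP 11.1 states that "The number and percentage of participants reporting TEAEs in each study intervention group will be tabulated by system organ class and preferred term". Treatment-related TEAEs are handled the same way. SAEs and AEs leading to discontinuation get summary tables of participants when at least 5 report such events. An AE more than 35 days after the last dose is not a TEAE. No rate per unit of exposure and no time-to-event summary is specified.

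**Length of treatment.** In the schematic text of SAP 4.1, "the Titration Period may end at Week 18, 24, 30, or 36". The trigger for extension is that "If participants' TSH levels are out of normal reference range at Visit 5a, participants' doses can be up- or down-titrated". After that, "The Stabilization Period is 12 weeks in duration", so for completers "the Stabilization Period may end at Week 30, 36, 42, or 48". Participants who have not normalised after three additional titrations do not enter Stabilization.

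**Periods.** Protocol 9.4.2 says the safety analysis will be "based on a whole study and different periods separately and will be fully defined in the SAP". SAP 11.0 says "The safety analysis will be performed on the Safety and Safety-T3 Populations"; it names populations but no periods.

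**Exposure.** SAP 9.1 summarises patient-years by treatment, "defined as exposure to the study treatment in years". Treatment duration there runs from first dose to last dose. Mean daily dose (9.1) and compliance (9.2) are summarised by period, and SAP 16.2 defines where Titration ends and Stabilization begins.

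**The concern.** The chance of recording at least one event grows with time observed. Here that time is decided after randomisation by how well TSH is controlled. The arms do not start alike: controls stay on the T4 dose on which they are already euthyroid, while the other arm is switched through a conversion table. More extension in the switched arm is plausible and would raise its crude percentages without any higher risk. More early stopping in that arm would lower them.

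Similar safety and tolerability is a stated clinical hypothesis (Protocol 4.1.1), and a safe dose conversion is part of the objectives (SAP 5.0). Dose changes happen in Titration and are not allowed in Stabilization, so pooled AE tables also cannot show which phase carries the events.

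**Working it through.** **1. The plan's own durations.** Titration 18 to 36 weeks plus Stabilization 12 weeks: 18 + 12 = 30 and 36 + 12 = 48 weeks, as in the protocol synopsis. Adding up to 3 weeks of screening gives 33 and 51, as in SAP 4.1. Both reproduce. Treatment varies 48/30 = 1.6-fold among completers. With the 35-day (5-week) tail, the TEAE window is 35 to 53 weeks, a ratio of 53/35 = 1.51.

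**2. Effect on one participant.** Assume a constant weekly hazard h, so P(at least one event) = 1 − exp(−h·t). Set h so that 5%, 20% or 50% have an event in 35 weeks. Over 53 weeks these become 7.5%, 28.7% and 65.0%.

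**3. Effect between arms, equal hazard.** The documents give no shares, so these are assumptions. Shares are for Titration ending at Week 18 / 24 / 30 / 36 / never normalised, with windows of 35 / 41 / 47 / 53 / 41 weeks (the last assumes a final dose at Week 36).

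| Assumed mix (%) | Mean window, weeks | 5% event | 20% event | 50% event |
|---|---|---|---|---|
| T4: 90/6/2/1/1 | 35.84 | 5.12% | 20.41% | 50.75% |
| Armour: 80/12/4/2/2 | 36.68 | 5.23% | 20.83% | 51.51% |
| Armour: 70/15/7/4/4 | 37.70 | 5.37% | 21.33% | 52.40% |
| Armour: 50/25/12/8/5 | 39.68 | 5.65% | 22.30% | 54.15% |

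The true rate ratio is 1.0 throughout. The spurious difference runs from 20.83 − 20.41 = 0.4 to 54.15 − 50.75 = 3.4 points for the two more common events, and from 0.1 to 0.5 points for the 5% event.

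**4. A simpler model.** Take 40% to 60% risk by 30 weeks, 9 to 12 extra weeks for anyone extended, and no tail. An extended participant gains 8.5 to 12.3 points. If 30% versus 10% are extended, the gap is 0.20 × (8.5 to 12.3) = 1.7 to 2.5 points. If 50% versus 10%, it is 0.40 × (8.5 to 12.3) = 3.4 to 4.9 points.

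**5. Direction.** Let 10% or 20% of the 70/15/7/4/4 arm stop at Week 12 (window 17 weeks), with no early stopping on T4. For the 50% event the crude figure falls from 52.40% to 50.02% or 47.64%, against 50.75% on T4. The sign reverses, to −0.7 or −3.1 points.

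**6. Scale.** The standard error of a difference at 142 per arm is √(2 × 0.25/142) = 5.9 points at 50% and √(2 × 0.16/142) = 4.7 points at 20%.

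**7. Would a split by period alone be enough?** The variable time lies wholly in Titration, where the range is 36/18 = 2.0-fold. Under the same assumptions (50% event, T4 mix against 50/25/12/8/5, tail kept only for the never normalised), crude Titration percentages are 31.22% and 36.68%. That is a gap of 5.5 points, larger than the 3.4 for the whole study.

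**8. Would the SAP 9.1 patient-years do as denominator?** They stop at last dose while events count for 5 more weeks. With equal hazards the rate is inflated by 35/30 = 1.17 for the shortest completers, 53/48 = 1.10 for the longest and 17/12 = 1.42 for someone stopping at Week 12. With time at risk matched to the event window, the rate ratio is 1.0 in every constant-hazard case above.

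**The case against.** **Participant percentages are conventional, and nothing is tested.** This stands. The AE tables are descriptive, no AE margin or test is planned, and treatment duration and patient-years are shown by arm, so a reader could notice an exposure imbalance. That lowers the severity. It does not tell the reader how far a given percentage has been moved.

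**The size is all assumption and lies below sampling error.** This also stands. No AE rate and no extension rate appears in the documents. The distortion is nevertheless systematic, and a denominator removes it cheaply.

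**The by-period tables may exist.** SAP 17.0 (changes from the protocol) is redacted, and SAP 4.0 places table specifications in a separate document. A reader might infer that the by-period analysis has been dropped. The documents show only that visible Section 11 does not define it, although the protocol says the SAP will define it in full.

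**Section 11 is not whole-study throughout.** Correct. Laboratory and vital-sign results are shown at each assessment, and the ECG section has interim summaries and refers to a pre-dose baseline at each period. The gap concerns AEs.

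**A Stabilization table is not a clean comparison.** Correct. Its planned length is equal, but only participants whose TSH normalised enter it.

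**Conclusion.** A minor point that holds. SAP 11.1 has no exposure adjustment for AEs although treatment length ranges 1.6-fold among completers according to a post-randomisation TSH result, and the protocol's by-period commitment is not visible for AEs in Section 11. For events seen in 20% or more of participants, the spurious between-arm difference is about 0.4 to 5 points, in either direction. This rests on a constant and equal hazard and on assumed shares extended or stopping early.

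Two stronger readings are not supported. One is that the tables will make Armour Thyroid look worse: early stopping can reverse the sign, and no extension rates are given. The other is that splitting by period would remove most of the problem: a crude Titration table keeps the artefact in relatively larger form, and the Stabilization table loses the fully randomised comparison. The exposure-adjusted rate is therefore the main part of the remedy.

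**What to change.** **In SAP 11.1, alongside the percentages,** add exposure-adjusted rates for overall TEAEs, SAEs and TEAEs leading to discontinuation. Use either participants with a first event per 100 patient-years at risk or events per 100 patient-years. Define time at risk to match the TEAE window: from first dose to the earlier of 35 days after last dose and end of follow-up, censored at the first event for first-event rates. Do not reuse the treatment-only patient-years of SAP 9.1 as the denominator.

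**Also in SAP 11.1,** add AE tables for Titration and Stabilization as Protocol 9.4.2 states. Assign events by onset date using the boundaries in SAP 16.2, and say how events are assigned for participants who never reach Visit 6. Give exposure-adjusted rates for Titration. Footnote the Stabilization table to say that it includes only participants whose TSH normalised and is not a fully randomised comparison. If these tables are already specified elsewhere, a cross-reference is enough.

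**Cost.** A few more safety tables and one derived time-at-risk variable. No change to design or data collection.

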## 11.2

## CLINICAL LABORATORY PARAMETERS

Descriptive statistics for clinical laboratory values (in SI units) at baseline (screening) and changes from baseline at each assessment will be presented by study intervention for each clinical laboratory assessment.

 
Laboratory Assessments
 
		
 
Parameters
 
		
Thyroid-related	
 
Serum TSH, T4, T3, FT4, and FT3
 
			
Thyroglobulin and anti-thyroglobulin	
 
Thyroglobulin and anti-thyroglobulin testing only applicable for participants who have undergone total thyroidectomy for treatment of thyroid cancer
 
			
Hematology	Platelet count	RBC indices: MCV	WBC count with differential (absolute): Neutrophils	
	RBC count	MCH	Lymphocytes	
	Hemoglobin	MCHC	Monocytes	
	Hematocrit	%Reticulocytes	Eosinophils	
			Basophils	
Clinical Chemistry	BUN	Potassium	AST	Total, direct and indirect bilirubin
	Creatinine	Sodium	ALT	Total protein
	Glucose	Calcium	Alkaline phosphatase	Cholesterol, chloride, albumin
	HbA1c			
Routine Urinalysis a	
 
Specific gravity
 
pH, glucose, protein, blood, ketones
 
Microscopic examination (if blood or protein is abnormal)
 
			
Pregnancy Test a	
 
Urine and serum test (females of CBP)
 
			

ALT = alanine aminotransferase; AST = aspartate aminotransferase; BUN = blood urea nitrogen; CBP = childbearing potential; FT3 = free T3; FT4 = free T4; MCH = mean corpuscular hemoglobin; MCHC = mean corpuscular hemoglobin concentration; MCV = mean corpuscular volume; RBC = red blood cell; T3 = liothyronine; T4 = levothyroxine; TSH = thyroid-stimulating hormone; WBC = white blood cell

a Serum pregnancy tests will be standard at the Screening Visit (Visit 1) and Visit 7; local urine testing will be standard for all other visits, as specified in the schedule of activities, unless serum testing is required by local regulation or IRB/IEC.

Clinical laboratory test values will be considered potentially clinically significant (PCS) if they meet either the lower-limit or higher-limit PCS criteria listed in [Table 11-1](#). The number and percentage of participants who have PCS post-baseline clinical laboratory values will be tabulated by study intervention at each assessment. The percentages will be calculated relative to the number of participants who have available non-PCS baseline values and at least 1 post-baseline assessment. The numerator will be the total number of participants with at least 1 PCS post-baseline value. A supportive listing of participants with PCS post-baseline values will be provided for the Safety and Safety-T3 Populations.

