5.2. Exclusion Criteria

Participants are excluded from the study if any of the following criteria apply:

1.	Medical Conditions
1.01	Any clinical condition or previous surgery that might affect the absorption, distribution, biotransformation, or excretion of Armour Thyroid or synthetic T4.
1.02	History of alcohol or other substance abuse within the previous 5 years.
1.03	Known or suspected allergy or intolerance to any ingredients of Armour Thyroid, including its excipients, levothyroxine (T4), other thyroid replacement medications, or pork products.
2.	Prior/Concomitant Therapy
2.01	Have taken any prohibited concomitant medication that cannot meet the requirements prior to Baseline (Visit 2) as outlined in Section 6.5.1 .
2.02	Have received active treatment with an investigational drug within 30 days or 5 half-lives, whichever is longer, of Screening Visit (Visit 1).
2.03	Participant cannot be taking a daily dose of synthetic T4 that exceeds 200 µg at Screening Visit (Visit 1).
3.	Prior/Concurrent Clinical Study Experience
3.01	Current enrollment in an investigational drug or device study or participation in such a study within 60 days of entry into this study.
4.	Diagnostic Assessments
4.01	Clinically significant results according to the Investigator or designee, on physical examination, medical history, ECG, hematology, clinical chemistry, or urinalysis that may put the participant at significant risk, may confound the study results, or may interfere significantly with the participant's participation in the study.
4.02	Sitting systolic BP [≥ 140 mm Hg or ≤ 90 mm Hg] or sitting diastolic BP [≥ 90 mm Hg or ≤ 50 mm Hg] at the Screening Visit. Note: A total of 3 readings of BP and pulse will be taken. The first reading should be rejected. If either the second or third reading meets exclusion criteria, the participant should be excluded.

Armour Thyroid

4.03	Abnormal ECG results thought to be potentially clinically significant according to the Investigator or designee, or QT prolongation (QTcF \geq 450 msec for male participants or \geq 470 msec for female participants) at the Screening Visit (Visit 1).
5.	Other
5.01	The participant has a concurrent disease, condition, or is in a situation which, in the Investigator's opinion, may put the participant at significant risk, may confound the study results, or may interfere significantly with the participant's participation in the study.

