## **4.0**

## **INTRODUCTION**

This statistical analysis plan (SAP) provides technical and detailed elaboration of the statistical analyses of the efficacy and safety data that will be performed for Study 3014-201-002 as outlined and/or specified in a final protocol dated 28 May 2019 and the most recent amendment dated 16 Jan 2020. Specifications of tables, listings and figures are provided in a separate document.

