**Table 11-3** **Criteria for Potentially Clinically Significant Electrocardiographic Values**

Parameter	Unit	Criterion Value a	Change from Baseline a
QRS duration	msec	$\geq 150$	—
PR interval	msec	$\geq 250$	—
QTcF interval for male	msec	$> 450$	Increase of $> 60$
QTcF interval for female	msec	$> 470$	Increase of $> 60$

a post-baseline (end-of-study or post-dose) value will be considered potentially clinically significant if it meets the criterion value or the change from baseline or pre-dose value.

PCS = potentially clinically significant;

QTcF = QT interval/(60/RR)1/3.

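### As written, the PCS percentages in SAP 11.2 and 11.4 (QRS and PR) exclude abnormal baselines from the denominator but not the numerator

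*SAP*

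**What the plan says.** SAP 11.2 calculates laboratory PCS percentages "relative to the number of participants who have available non-PCS baseline values and at least 1 post-baseline assessment". The next sentence gives the numerator: "The numerator will be the total number of participants with at least 1 PCS post-baseline value". SAP 11.4 has the same pair of sentences for ECG, and SAP 11.3 has it for vital signs. Protocol 9.4.2.2, 9.4.2.3 and 9.4.2.4 carry the pair too; there, only the PCS criteria are left to the SAP.

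What counts as PCS differs by data type:

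- **Laboratory.** Values are PCS "if they meet either the lower-limit or higher-limit PCS criteria listed in" Table 11-1. That table has a lower and a higher limit and no change-from-baseline column.
- **ECG.** Under the footnote to Table 11-3, a "value will be considered potentially clinically significant if it meets the criterion value or the change from baseline or pre-dose value". QRS and PR have a criterion value and no change criterion.
- **Vital signs.** Table 11-2 requires the observed value and the change from baseline together.

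SAP 16.3 uses every post-baseline assessment to determine PCS status and adds no baseline condition.

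**The concern.** Limiting the denominator to non-PCS baselines serves one purpose: to make the percentage describe abnormality that appeared after treatment began. That works only if the numerator is drawn from the same participants. Read literally, it is not. Someone already past a limit before the first dose, and still past it later, adds one to the numerator and nothing to the denominator.

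The table would then report pre-existing abnormality as post-baseline PCS. If such participants fall unevenly across the arms, it would also show a difference that has nothing to do with treatment. The SAP takes the opposite line for adverse events: in SAP 11.1 an event present before dosing is treatment-emergent only if it was present "but increased in severity or became serious on or after the date of the first dose of study intervention". That rule governs a different kind of data, so there is no contradiction, but it shows the same aim of separating new from old.

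**Working it through.** The plan states no PCS rate, so there is no figure to reproduce. The check is of the definition, followed by its arithmetic.

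**1. Can a baseline be PCS and stay PCS?** Table 11-1 has 19 chemistry, 13 hematology and 2 urinalysis rows: 19 + 13 + 2 = 34. Five of these (triglycerides, magnesium, bicarbonate, phosphate, uric acid) are not in the SAP 11.2 panel, whose chemistry block includes, for example, "Cholesterol, chloride, albumin". That leaves 34 − 5 = 29 collected tests, all judged on the observed value alone. Some limits lie close to normal, such as urea above 1.2 × ULN and hemoglobin below 0.9 × LLN. QRS and PR are also absolute. So yes.

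**2. Do the entry rules prevent it?** Protocol 5.2 (exclusions 4.01 and 4.03) and 8.2.4 exclude on investigator judgement. For ECG the first clause of 4.03 reads "Abnormal ECG results thought to be potentially clinically significant according to the Investigator or designee". This reduces the number of such baselines, but it does not apply the Table 11-1 or 11-3 limits, so it does not guarantee that there are none.

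**3. Formula.** For one test in one arm, let

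- N = 142, the approximate number per arm (SAP 4.1), all assumed to have a baseline and later data;
- b = participants PCS at baseline;
- k = those of the b who are PCS again afterwards;
- m = new cases among participants whose baseline was not PCS;
- D = N − b.

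As written: (m + k)/D. Restricted to the denominator: m/D. Overstatement: k/D.

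**4. One participant.** b = k = 1, D = 142 − 1 = 141, and 1/141 = 0.71 percentage points.

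**5. Illustrations.** b and m are assumptions, and every baseline abnormality is taken to persist (k = b).

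| m | b = k | As written | Restricted |
|---|---|---|---|
| 0 | 3 | 3/139 = 2.2% | 0% |
| 0 | 7 | 7/135 = 5.2% | 0% |
| 3 | 0 | 3/142 = 2.1% | 3/142 = 2.1% |
| 3 | 3 | 6/139 = 4.3% | 3/139 = 2.2% |
| 3 | 7 | 10/135 = 7.4% | 3/135 = 2.2% |
| 3 | 14 | 17/128 = 13.3% | 3/128 = 2.3% |

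**6. Between arms.** With equal k/D the excess cancels in the difference. With m = 3 in both arms but b = k = 10 in one and 4 in the other, the written rule gives 13/132 = 9.8% against 7/138 = 5.1%. The restricted rule gives 3/132 = 2.3% against 3/138 = 2.2%.

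**7. Not a proportion.** Nothing caps the ratio at 100%. As an extreme to show the point, m = 0 and b = k = 72 gives 72/70 = 103%.

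**The case against.** The strongest reply is that the two sentences describe one percentage, so the numerator is naturally counted within the set just defined, and the second sentence only says what an event is. That is probably what the authors meant; the baseline restriction has little purpose otherwise. But the sentence speaks of a total number, and no other text restricts it. Two programmers could follow the SAP in good faith and produce different tables.

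A second reply is that SAP 4.0 says "Specifications of tables, listings and figures are provided in a separate document". Those specifications may already carry the filter. This stands: whether any table would come out wrong cannot be settled from the protocol and SAP.

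A third is that the size is not shown. This also stands. The count of 29 tests shows where the mismatch could arise, not that any participant has a PCS baseline, and the entry rules probably leave very few for QRS and PR.

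Some stronger readings are tempting but not supported:

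- *That one arm is systematically disadvantaged, or that only the arm with more such participants is affected.* Every arm with k of at least 1 is overstated. Baseline status precedes 1:1 randomization, so no direction is expected.
- *That vital signs share the fault.* They carry the same sentence, but Table 11-2 requires a change, so an unchanged baseline abnormality cannot count.
- *That missing baselines add to it.* Laboratory tests and ECG are scheduled at both Visit 1 and Visit 2, and SAP 16.1 takes the last available value, so this route is nearly empty.
- *That the wording is the SAP's alone, because the protocol defers detail to it.* Protocol 9.4 and 9.4.2 do defer detail, but 9.4.2.2 and 9.4.2.4 state this numerator and denominator themselves.

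**Conclusion.** The point holds as a fault in the written rule, confined to descriptive safety tables. Followed exactly, SAP 11.2, and SAP 11.4 for QRS and PR, overstate the PCS percentage by k/D in every arm with k of at least 1: about 0.7 points for one participant at 142 per arm. The between-arm difference is distorted only if k/D differs by arm. The size in this trial is unknown, because the documents give no baseline PCS frequency and no forecast of k is made here. The same tables are produced for the Safety-T3 Population, a subset of unstated size, where each such participant weighs more.

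The conclusion assumes that the SAP sentence is followed as written and that the table specifications do not correct it. QTcF is left out: it too has a stand-alone criterion value, but the screening exclusion makes a PCS baseline unlikely, though a Visit 2 reading could still supply one. No hypothesis test uses PCS rates, the primary and secondary conclusions are untouched, and listings and changes from baseline remain available. This is worth correcting but is not serious.

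**What to change.** - In SAP 11.2 and 11.4, define the numerator as the number of participants **in the denominator** who have one or more PCS values after baseline.
- Use the same sentence in SAP 11.3, so that the three parallel sections read alike, although the result there should not change.
- Record in SAP 17.0 that this clarifies protocol 9.4.2.2 to 9.4.2.4, so that the difference in wording is disclosed. The content of SAP 17.0 is not visible in the public copy.
- Apply the filter in the table specifications, or confirm that it is already there.
- Keep participants with a PCS baseline in the listings, so that nothing is lost from view.

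The cost is one sentence in each of three SAP sections, one entry in SAP 17.0, and a filter in table programming before database lock. No new data are needed.
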